8.0 Statistical Considerations

The primary outcome for this study is the false negative rate of PET/CT and/or sentinel lymph node mapping for detecting positive lymph nodes in women with high risk of endometrial cancers as compared with pathological findings as the gold standard.

We will also estimate the concordance, sensitivity, specificity, positive predictive value (PPV) and negative predictive value (NPV) for each method (PET/CT and sentinel lymph node mapping), as well as the combination of the 2 methods.

Futility Monitoring

We will enroll 100 evaluable patients. We will monitor the false negative rate for the sentinel lymph node mapping procedure using the method described by Thall et al. [9], and we will stop using the sentinel lymph node mapping procedure if we have reason to believe that the false negative rate for this procedure is more than 10%. However, we will continue to use the PET/CT procedure for detecting positive lymph nodes for all patients.

We will monitor the false negative rate only for those patients with positive lymph nodes. We expect about 25% of patients will have positive lymph nodes, and we expect the false negative rate to be at most 10%, therefore, we expect about 70 patients will test negative for positive lymph nodes.

Formally, we will assume a uniform prior distribution for the false negative rate, and we will stop using the sentinel lymph node mapping procedure if $\Pr(\text{false negative rate} > 10\% | \text{data}) > 0.95$. That is, if there is more than a 95% chance that the false negative rate is more than 10% we will stop using the sentinel lymph node mapping procedure. We will evaluate the monitoring rule after each cohort of 5 patients with positive lymph nodes. This decision rule gives the following stopping rule.

Stop using the sentinel lymph node mapping procedure if

$$[\# \text{ of patients with false negative finding}] / [\# \text{ of patients with positive lymph nodes}] \geq 2/5, 3/10, 4/15, 5/20, 5/25, 6/30, 7/35.$$

The operating characteristics of this stopping rule are shown in the table below and are based on 1,000 simulations.

False Negative Rate	Probability of Stopping Early	Sample Size		
		P ₂₅	P ₅₀	P ₇₅
25.0%	0.701	5	10	25
20.0%	0.530	5	20	25
15.0%	0.314	15	25	25
10.0%	0.139	25	25	25
5.0%	0.032	25	25	25

Sample Size

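### The operating-characteristics table counts stops only at 5 to 20 node-positive patients, so it does not describe the seven-look rule (5 to 35) that it claims to describe

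*Combined protocol and SAP*

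**What the plan says.** The futility monitoring text in section 8.0 sets a Bayesian rule for the FNR of sentinel node mapping among node-positive patients.

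- Prior: "we will assume a uniform prior distribution for the false negative rate".
- Criterion: "if there is more than a 95% chance that the false negative rate is more than 10% we will stop" using the mapping procedure.
- Schedule: "We will evaluate the monitoring rule after each cohort of 5 patients with positive lymph nodes".
- Boundaries, as false negatives over node-positives: "2/5, 3/10, 4/15, 5/20, 5/25, 6/30, 7/35".
- Expected size: "We will enroll 100 evaluable patients", and "We expect about 25% of patients will have positive lymph nodes".

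The boundary list is followed at once by the table, introduced with "The operating characteristics of this stopping rule are shown in the table below and are based on 1,000 simulations". Its first row reads "25.0% 0.701 5 10 25": true FNR, probability of stopping early, and the 25th, 50th and 75th percentiles of sample size. No percentile in any row exceeds 25. Section 8.0 states no maximum number of node-positive patients. Nor does it say that crossing the boundary at 25, 30 or 35 was left out of the stopping probability.

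**The concern.** The table is introduced as describing the rule just listed, which has looks at 25, 30 and 35 positives. A simulation of that rule could not have all its upper percentiles at 25 when stopping is uncommon: at an FNR of 5 or 10%, most runs would continue to 35. That suggests the simulation was cut short.

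The table is the plan's only evidence of how the rule behaves. Readers use it to judge two risks: abandoning mapping when its FNR is at the acceptable 10%, and keeping it when its FNR is well above that. If looks are missing, both stopping probabilities are too low.

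**Working it through.** **Inputs.** Uniform prior, 10% threshold, 0.95 cutoff, looks every 5 node-positives, seven boundaries, 100 evaluable patients, 25% expected node-positive, 1,000 simulations. All come from section 8.0. One assumption is added where marked: the number of node-positives N follows Binomial(100, 0.25).

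**Step 1: the boundaries.** After r false negatives in n positives the posterior is Beta(1+r, 1+n−r). The boundary is the smallest r with Pr(FNR > 0.10 | data) > 0.95.

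| n | boundary r | posterior at r | posterior at r−1 |
|---|---|---|---|
| 5 | 2 | 0.984 | 0.886 |
| 10 | 3 | 0.981 | 0.910 |
| 15 | 4 | 0.983 | 0.932 |
| 20 | 5 | 0.986 | 0.948 |
| 25 | 5 | 0.960 | 0.888 |
| 30 | 6 | 0.969 | 0.917 |
| 35 | 7 | 0.976 | 0.937 |

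All seven reproduce.

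**Step 2: stopping probabilities.** The count of false negatives is carried forward five patients at a time with Binomial(5, p) increments. Paths at or above the boundary are removed at each look and their probability is added to the stopping total. For p = 0.25, the first look gives 1 − 0.75⁵ − 5(0.25)(0.75⁴) = 1 − 0.2373 − 0.3955 = 0.3672. The running total over the seven looks is then 0.367, 0.537, 0.638, 0.705, 0.827, 0.865, 0.889. The table's 0.701 fits the fourth value, the look at 20.

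| True FNR | Table | Looks 5–20 | Looks 5–25 | Looks 5–35 |
|---|---|---|---|---|
| 25% | 0.701 | 0.705 | 0.827 | 0.889 |
| 20% | 0.530 | 0.521 | 0.650 | 0.721 |
| 15% | 0.314 | 0.316 | 0.407 | 0.458 |
| 10% | 0.139 | 0.138 | 0.172 | 0.187 |
| 5% | 0.032 | 0.030 | 0.033 | 0.034 |

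A check with 200,000 simulated paths agreed with the exact values to within 0.002.

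**Step 3: can simulation error explain it?** With 1,000 runs the standard error is √(p(1−p)/1000). Against looks 5–20, every row is within 0.6 standard errors. Against looks 5–25, the 25% row gives (0.701 − 0.827)/√(0.827 × 0.173/1000) = −0.126/0.012, about −10.5; the 20, 15 and 10% rows are about 8, 6 and 3 standard errors low. Against looks 5–35, the first four rows are about 19, 13, 9 and 4 standard errors low. The 5% row cannot separate the versions.

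**Step 4: the percentiles.** With a maximum of 25, every percentile in the table is reproduced. With a maximum of 35, the 75th percentile at FNR 20%, the 50th and 75th at 15%, and all three at 10% and 5% would be 35. The table shows 25 in each.

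**Step 5: what the rule would do with 100 patients.** With N ~ Binomial(100, 0.25), P(N ≥ 25) = 0.54, P(N > 25) = 0.45, P(N ≥ 30) = 0.15 and P(N ≥ 35) = 0.016. Averaging the cumulative stopping probability over N, with every completed look applied:

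| True FNR | Table | Averaged over N | Difference |
|---|---|---|---|
| 25% | 0.701 | 0.770 | 0.069 |
| 20% | 0.530 | 0.591 | 0.061 |
| 15% | 0.314 | 0.367 | 0.053 |
| 10% | 0.139 | 0.157 | 0.018 |
| 5% | 0.032 | 0.032 | 0.000 |

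The look at 25 matters most. The boundary stays at 5 false negatives between 20 and 25 positives, so this one look adds 0.827 − 0.705 = 0.122 at an FNR of 25%.

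**The case against.** The best defence is that the column concerns early stopping and the plan expects 25 positives among 100 patients. If the study ends at the 25th positive, a crossing there leaves no mapping to stop. Only looks 5 to 20 then count as early, and 30 and 35 are contingency values in case prevalence runs high. The cap can be inferred from the percentiles. On this reading the arithmetic is right and the fault is an unstated assumption.

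This is a plausible account of how the table arose, and its numbers are correct for that capped design. It does not make the table a description of the listed rule. Enrolment ends at 100 evaluable patients, not at 25 positives, and with probability 0.45 more positives follow the 25th. Even if a crossing counts only when at least one positive patient is still to come, averaging over N gives 0.753, 0.574, 0.355, 0.153 and 0.032. The table is still low by 0.052, 0.044 and 0.041 at FNR 25, 20 and 15%.

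Three points on the other side stand. The figures through 35 need an outcome with probability 0.016, so they are an upper bound. At an FNR of 10% the realistic shift is 1.4 to 1.8 points, little more than the table's own simulation standard error of about 1.1 points. And at high FNR the table errs by underselling the rule's ability to catch a poor procedure.

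**Conclusion.** The concern holds. The table gives the stopping probabilities of a four-look rule capped at 25 node-positives, while the text attributes them to a seven-look rule running to 35. That identification rests on exact calculation from the plan's own inputs, and the stopping probabilities and the percentiles agree on it.

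The practical size depends on the assumption that node-positives are Binomial(100, 0.25). On that basis the chance of stopping is understated by about 5 to 7 points at FNR 15 to 25%, by about 2 points at 10%, and not at all at 5%. If exactly 25 positives are reached and that look is counted, the shortfalls at FNR 25, 20, 15 and 10% are about 13, 12, 9 and 3 points. The boundaries, prior, cutoff and look schedule are not in error.

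**What to change.** Preferably, replace the table with exact values for the rule as listed. Treat the number of node-positives as random (100 patients, 25% prevalence) and report the probability of crossing at any look reached. State how a crossing at the last look is counted.

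Alternatively, keep the table, say that it covers looks at 5, 10, 15 and 20 with a maximum of 25 positives, and add the values through 25 and through 35 with a note that the latter are an upper bound.

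Either way the cost is one table or a short addition; no boundary, sample size or procedure changes. The one unwelcome effect is that the stated probability of wrongly stopping at an FNR of 10% rises from 13.9% to about 16% averaged over N, or 17% through 25 and 19% through 35.

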If we complete the study with 1 false negative with the sentinel lymph node mapping procedure among 25 patients with positive lymph nodes, then a 90% credible interval for the false negative rate for that procedure will be 1.4% to 13.8%.

With a sample size of 100 evaluable patients we will be able to estimate the concordance between either of the 2 procedures, or the combination of the 2 procedures, and pathologic findings with a 95% confidence bound of at most 10%. We expect approximately 25% of patients will be found to have positive lymph nodes. The table below illustrates a possible study outcome with an 8% false negative rate with 25% of patients with positive lymph nodes.

Table 2. 100 Patients, 25% Lymph Node Positive, 10% False Negative

Test		Lymph Nodes		Total
		Negative	Positive	
	Positive	7	23	30
	Negative	68	2	70
	Total	75	25	100

For the study outcome illustrated in Table 2 we would have the following results:

Sensitivity = 92% (95% CI 72% - 99%),

Specificity = 91% (95% CI 81% - 96%),

PPV = 77% (95% CI 57% - 89%),

NPV = 97% (95% CI 89% - 99%).

Analysis

We will use descriptive statistics to summarize demographic and clinical characteristics of patients.

Once the trial is complete we will estimate the false negative rate for each procedure (PET/CT, sentinel lymph node mapping) and for the combination of the 2 procedures with 90% credible intervals. We will also report the posterior probability that the false negative rate is > 10% for each procedure and for the combination of the 2 procedures.

We will also estimate with 95% confidence intervals the concordance, sensitivity, specificity, PPV, and NPV for each procedure and for the combination of the 2 procedures using pathologic findings as the gold standard.

We will use logistic regression methods to model the logit of the probability of metastatic disease at the time of surgical staging as a function of CA-125 level, HE4 level, and other metabolic parameters including tumor intensity, metabolic tumor volume, and total lesion glycolysis. And we will estimate the odds ratio of the association between these factors and metastatic disease with a 95% confidence interval. We will similarly model the logit of the probability of locoregional spread as a function of these factors. We will also estimate the correlations among these factors.

We will tabulate morbidity and mortality data, including intra-operative and post-operative complications.

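### The illustrated 90% credible interval for the sentinel mapping false negative rate (1 miss in 25) prints an upper limit of 13.8%; the plan's uniform prior gives 17.0%

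*Combined protocol and SAP*

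**What the plan says.** All the relevant text is in section 8.0 of the combined protocol and SAP.

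- **Futility Monitoring** fixes the prior: "we will assume a uniform prior distribution for the false negative rate". It also fixes the denominator: "We will monitor the false negative rate only for those patients with positive lymph nodes". The benchmark is a rate of 10%, and sentinel mapping stops if the posterior probability of exceeding it is above 0.95.
- **Sample Size** supposes "1 false negative with the sentinel lymph node mapping procedure among 25 patients with positive lymph nodes" at the end of the study, and states that "a 90% credible interval for the false negative rate for that procedure will be 1.4% to 13.8" percent. It names neither the prior nor the type of interval.
- **Analysis** says the final false negative rates will be estimated for each procedure and "for the combination of the 2 procedures with 90% credible intervals". The illustration is therefore at the level that the final report will use.

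**The concern.** The false negative rate is the primary outcome, and this sentence is the only place where the plan shows how precisely a credible interval will estimate it. One miss in 25 is an observed rate of 4%. With so few events the posterior is strongly right-skewed, so the upper limit carries most of the information, and 13.8% looked too low for a uniform prior.

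A reader compares that limit with the 10% benchmark. As printed, it lies 3.8 points above the benchmark (13.8 − 10.0). If the true limit is 17.0%, it lies 7.0 points above, and the plan promises more precision than 25 node-positive patients can deliver. There is also a practical point: if the figure came from a faulty calculation, the same calculation might be used for the final intervals.

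**Working it through.** **Inputs (all from section 8.0)**

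- Prior: uniform, that is Beta(1, 1) (Futility Monitoring).
- Data: x = 1 false negative in n = 25 node-positive patients (Sample Size).
- Level: 90% (Sample Size and Analysis).
- Printed limits: 1.4% and 13.8%.

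**Step 1. Posterior.** Beta(1 + x, 1 + n − x) = Beta(2, 25).

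**Step 2. Equal-tailed limits.** For this posterior the upper-tail probability has a closed form:

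Pr(rate > p) = (1 − p)^26 + 26·p·(1 − p)^25

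| p | (1 − p)^26 | 26·p·(1 − p)^25 | Pr(rate > p) |
|---|---|---|---|
| 0.01384 | 0.6960 | 0.2540 | 0.950 |
| 0.16983 | 0.0079 | 0.0421 | 0.050 |
| 0.014 (printed lower) | 0.6931 | 0.2559 | 0.9490 |
| 0.138 (printed upper) | 0.0210 | 0.0876 | 0.1087 |
| 0.10 (benchmark) | 0.0646 | 0.1867 | 0.2513 |

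The 5th percentile is 1.38%, which rounds to the printed 1.4%. The 95th percentile is 16.98%, not 13.8%.

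**Step 3. What the printed interval contains.** 0.9490 − 0.1087 = 0.8403. It therefore holds 84.0% of the posterior, with 5.1% below and 10.9% above. Its width is 13.8 − 1.4 = 12.4 points, against 17.0 − 1.4 = 15.6.

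**Step 4. Does the uniform prior match the rest of the plan?** The table gives Pr(rate > 10%) at each printed stopping boundary and at one miss fewer.

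| Boundary | At the boundary | One miss fewer |
|---|---|---|
| 2/5 | 0.984 | 0.886 |
| 3/10 | 0.982 | 0.910 |
| 4/15 | 0.983 | 0.932 |
| 5/20 | 0.986 | 0.948 |
| 5/25 | 0.960 | 0.888 |
| 6/30 | 0.969 | 0.917 |
| 7/35 | 0.977 | 0.937 |

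All seven boundaries are the smallest counts that pass 0.95, exactly as printed.

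**Step 5. Could another method explain the printed pair?**

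| Method, 1/25 | Interval |
|---|---|
| Uniform prior, 90% equal-tailed | 1.4% to 17.0% |
| Uniform prior, 90% highest-density | 0.4% to 14.3% |
| Uniform prior, 80% equal-tailed | 2.1% to 14.2% |
| Uniform prior, 5th to 90th percentile | 1.4% to 14.2% |
| Jeffreys prior, 90% equal-tailed | 0.7% to 14.6% |
| Haldane prior, 90% equal-tailed | 0.2% to 11.7% |
| Beta(1, 9) prior, 90% equal-tailed | 1.1% to 13.2% |
| Clopper-Pearson, 90% | 0.2% to 17.6% |
| Wilson, 90% | 0.9% to 16.1% |

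None gives both limits. A search over 0 to 7 misses in 10 to 100 patients (uniform or Jeffreys prior, equal-tailed 90%, rounded to 0.1 point) also found no match, so a mistyped count does not explain the figure.

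**Step 6. A sense of scale.** With one miss in n, the upper limit is the 95th percentile of Beta(2, n): 14.0% at n = 31 and 13.6% at n = 32. An upper limit of 13.8% or less therefore needs 32 node-positive patients, or 32 / 0.25 = 128 evaluable patients at the plan's 25% positivity. The plan sets no target for this interval, so this is a yardstick and not a shortfall.

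**The case against.** **The figure drives nothing.** The sentence is a conditional illustration, and the final interval will be computed from the data. The precision statement that the plan ties to 100 patients is the one for concordance, not this one. The stopping boundaries, the enrolment and the posterior probability of 0.25 are unaffected, and with either upper limit 10% is not excluded. All of this stands, and it bounds the importance of the point. It does not make the figure correct.

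**The prior and interval type are inferred.** The uniform prior is stated for monitoring, and the illustration names neither a prior nor equal tails. A 1/25 result with a prior near Beta(1.35, 11.0) would reproduce the printed interval. That is true, but no such prior appears anywhere in the plan. The uniform prior is the only one stated, concerns the same rate, and gives the printed lower limit. If another prior was used, the plan would still need to state it.

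**Wide uncertainty is already visible.** The same subsection gives a 95% confidence interval of 72% to 99% for sensitivity at 2 misses in 25, which is 1% to 28% on the false negative scale. A careful reader is thus warned. But the count, the level and the kind of interval all differ, so it does not correct the credible interval.

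**Conclusion.** The concern holds. Under the plan's uniform prior and equal tails, 1 miss in 25 gives 1.4% to 17.0%. The printed upper limit is 3.2 points too low, and what is called a 90% interval holds 84.0% of the posterior probability. The error makes the precision of the primary outcome look better than it is. It is confined to one displayed figure.

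The conclusion rests on two assumptions: that the monitoring prior carries over to the illustration, and that the interval is equal-tailed. The matching lower limit supports both. How 13.8% arose cannot be told from the documents.

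**What to change.** In section 8.0, Sample Size, replace the printed interval with 1.4% to 17.0% and state that it is equal-tailed under a uniform prior. State the same prior and interval type under Analysis, so that the final 90% credible intervals follow one declared convention. If the sponsor intended a different prior, it should be stated and justified, and the interval recomputed from it. The sponsor should also check the calculation that produced 13.8% before it is used for the final analysis.

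Optionally, show the neighbouring outcomes under the same convention: 0.2% to 10.9% for 0/25 and 3.2% to 22.3% for 2/25.

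The cost is one corrected figure and a few words. The stated precision becomes less favourable. No extra patients are needed, and the stopping rule and planned analyses stay as they are.

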In larger, multi-institutional studies, including GOG 33, the risk of lymph node involvement was based on final tumor histology and depth of myometrial invasion. These data, however, are not available to the surgeon until the operation has been completed and the pathologist has carefully evaluated the surgical specimens. As a proxy for these, a multitude of pre-operative techniques including endometrial biopsy, trans-vaginal ultrasound, CT scan, and pre-operative CA125 have been evaluated and shown to be ineffective in predicting extra-uterine spread or lymph node metastasis [4-6]. While many current algorithms, including the algorithm used at the Mayo Clinic, base the decision for complete surgical staging on intra-operative frozen section, this is not universally available and is not always reliable [7]. In addition, the reproducibility of the diagnosis of endometrial cancer and endometrial hyperplasia among gynecologic pathologists is not always accurate [8].

For the above reasons, the gynecologic oncologists at Mayo Clinic recently re-evaluated the staging algorithm for endometrial cancer. After careful review of their consecutive endometrial cancer

cases over a thirteen year period (1984-1996), they have developed the following algorithm.

Mayo Surgical Guidelines for the treatment of endometrial cancer

Treatment includes hysterectomy, bilateral salpingo-oophorectomy, peritoneal cytology, bilateral pelvic and paraaortic lymphadenectomy (up to the renal vessels).

The lymphadenectomy can be omitted if:

- All of the following: no myometrial invasion, endometrioid histology, grade 1 or 2, no evidence of tumor outside the corpus (independent of tumor grade or tumor diameter).
- All of the following: endometrioid histology, grade 1 or 2, less than 50% myometrial invasion, tumor diameter less than or equal to 2 cm, and no evidence of tumor outside the corpus.
- Endometrioid histology (grade 3) with no myometrial invasion, tumor diameter less than or equal to 2 cm, and no evidence of gross tumor outside the uterus.

If non- endometriod histology (serous, clear cell) add complete omentectomy, appendectomy, and peritoneal biopsies.

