3.0 Patient Eligibility and Exclusions

3.1 Inclusion Criteria:

- 3.1.1** Histologically confirmed high grade endometrial cancer including grade 3 endometrioid, serous, clear cell, MMT or any mixed tumor containing one of these cell types
- 3.1.2** Patients with a grade 1/2 tumors and evidence of deep myometrial invasion or cervical involvement on preoperative imaging or physical exam
- 3.1.3** Candidate for surgery.
- 3.1.4** No evidence of peritoneal disease on preoperative imaging
- 3.1.5** Negative pregnancy test if of child-bearing age
- 3.1.6** No preoperative treatment for endometrial cancer including radiation or chemotherapy
- 3.1.7** Previous hormonal therapy is allowed

3.2 Exclusion Criteria:

- 3.2.1** Medical co-morbidities making surgery unsafe, as determined by the primary treating physician
- 3.2.2** Any contraindications to PET/CT or lymph node mapping (inability to control serum glucose to a value of <= 200 mg/dl for FDG-PET/CT)
- 3.2.3** Does not meet histologic criteria
- 3.2.4** Evidence of peritoneal or distant metastasis on preoperative imaging
- 3.2.5** Baseline creatinine (necessary for imaging studies)

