4.0 Research Plan/Methods

4.1 Patient Identification

All patients with a preoperative diagnosis of endometrial cancer, confirmed on the pathology report that meet the above eligibility criteria will be asked to participate in this study. They will be approached prior to surgery by the research nurse, study coordinator, or primary treating physician. If they agree to participate in the study and informed consent is obtained, patients will undergo a pre-operative evaluation by their primary physician to include. We will enroll up to 150 patients in order to accrue 100 evaluable patients. Patients will be considered evaluable if they have an attempt at sentinel lymph node mapping (i.e. cervical injection) and a full lymphadenectomy.

- Pre-operative informed consent

- Pre-operative laboratory assessment including CBC, electrolytes, bun, cr, CA125 and future research testing (as outlined in objective 1.2.4). Samples to be collected through this protocol or through the GYN Tumor Bank Protocol.
- Pre-operative CXR
- Pre-operative MRI or CT scan as per the primary surgeon
- Histologic confirmation of the pre-operative biopsy

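### The marker models in 8.0 carry no entry-group term, so their odds ratios cannot show whether CA-125, HE4 or a PET tumour parameter adds to what is known before surgery

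*Combined protocol and SAP*

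**What the plan says.** The Analysis part of 8.0 uses logistic regression for metastatic disease at surgical staging "as a function of CA-125 level, HE4 level, and other metabolic parameters including tumor intensity, metabolic tumor volume, and total lesion glycolysis". It will "estimate the odds ratio of the association between these factors and metastatic disease with a 95% confidence interval". A second outcome gets the same covariates: "We will similarly model the logit of the probability of locoregional spread as a function of these factors". Histology, grade and entry group appear in none of these models. No stratified or adjusted analysis is described elsewhere, and clinical characteristics are only summarised descriptively. The plan does not say whether markers are fitted singly or jointly.

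Section 3.1 admits two kinds of patient:
- Criterion 3.1.1 takes "Histologically confirmed high grade endometrial cancer" and lists the qualifying cell types.
- Criterion 3.1.2 takes lower-grade disease only under a further condition: "Patients with a grade 1/2 tumors and evidence of deep myometrial invasion or cervical involvement on preoperative imaging or physical exam"

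Both are settled before surgery. The work-up in 4.1 includes "Histologic confirmation of the pre-operative biopsy", and the further condition in 3.1.2 comes from imaging or examination. Section 2.0 says of larger studies that "the risk of lymph node involvement was based on final tumor histology and depth of myometrial invasion".

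The models serve objectives 1.2.4 (correlate CA-125 and HE4 with metastasis) and 1.2.6 (whether PET parameters of the primary tumour predict spread).

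**The concern.** Entry group is a candidate confounder by the protocol's own account. It is built from histology and depth of invasion, which section 2.0 links to nodal risk, and a serum marker or tumour uptake may plausibly differ between high-grade and grade 1/2 disease. An odds ratio from a model without entry group then blends two things: what the marker says within a group, and what the group already says.

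The difference matters for how the result is used. The background looks for tools that help decide before or during surgery who needs full staging. The surgeon making that decision already knows the biopsy and imaging findings that put the patient in 3.1.1 or 3.1.2. A marker that only repeats them offers nothing new. If the bias runs the other way, a marker that does add something could be missed.

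**Working it through.** **No figure to reproduce.** The plan gives no event count, power or sample size for the logistic models. What follows is illustration.

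**Inputs from 8.0.** 100 evaluable patients and about 25% node-positive, so 100 × 0.25 = 25 events. Node-positive count is a proxy, because no rate is stated for metastatic disease or locoregional spread.

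**Inputs assumed, not in the documents.** The share in the high-grade group (p), spread in each group (sH, sL), and the proportion with a raised marker in each group (mH, mL).

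**Step 1: two-level marker, no effect within either group.** The expected proportions are
- a (raised, spread) = p·sH·mH + (1−p)·sL·mL
- b (raised, no spread) = p·(1−sH)·mH + (1−p)·(1−sL)·mL
- c (not raised, spread) = p·sH·(1−mH) + (1−p)·sL·(1−mL)
- d (not raised, no spread) = p·(1−sH)·(1−mH) + (1−p)·(1−sL)·(1−mL)

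The crude odds ratio is ad/(bc). The within-group value is 1.0 by construction.

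Worked case with p = 0.50, spread 35% and 15%, marker raised in 80% and 20%, per 100 patients:
- a = 14 + 1.5 = 15.5
- b = 26 + 8.5 = 34.5
- c = 3.5 + 6 = 9.5
- d = 6.5 + 34 = 40.5
- OR = (15.5 × 40.5)/(34.5 × 9.5) = 627.75/327.75 = 1.92
- SE of log OR = √(1/15.5 + 1/34.5 + 1/9.5 + 1/40.5) = 0.473, giving a 95% interval of 0.76 to 4.84

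| p | Spread, high-grade / grade 1/2 | Marker raised, high-grade / grade 1/2 | Crude OR | 95% interval at n = 100 | Approx. chance of p < 0.05 |
|---|---|---|---|---|---|
| 0.75 | 28% / 16% | 70% / 30% | 1.22 | 0.48–3.12 | 7% |
| 0.70 | 30% / 13% | 75% / 25% | 1.50 | 0.58–3.90 | 13% |
| 0.60 | 33% / 13% | 70% / 20% | 1.68 | 0.67–4.20 | 20% |
| 0.50 | 35% / 15% | 80% / 20% | 1.92 | 0.76–4.84 | 28% |
| 0.70 | 25% / 25% | 75% / 25% | 1.00 | 0.40–2.52 | 5% |
| 0.70 | 21% / 35% | 75% / 25% | 0.73 | 0.29–1.81 | 11% |

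Overall spread is 25% in each row to within rounding.

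**Step 2: continuous marker.** Simulated logistic regression with n = 100, 25% spread overall, and a marker shifted by 1 to 2 within-group SDs in the high-grade group but unrelated to spread within groups (800 runs per setting, Monte Carlo error about 1–2 points):

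| High-grade share | Spread, high-grade / grade 1/2 | Crude OR per SD | Runs with p < 0.05 |
|---|---|---|---|
| 70% | 25% / 25% | about 1.0 | 4–5% |
| 85% | 27–28% / 10–15% | 1.08–1.18 | 5–9% |
| 70% | 29% / 15% | 1.15–1.19 | 8–17% |
| 70% | 31% / 10% | 1.23–1.30 | 15–30% |
| 50% | 35% / 15% | 1.24–1.31 | 16–36% |
| 50% | 40% / 10% | 1.38–1.53 | 30–69% |

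With 35% spread in the grade 1/2 group, the crude odds ratio falls to 0.76–0.94. Adding entry group brings false positives to about 3–5% in every setting, against a nominal 5%.

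**Step 3: cost in parameters.** Counting CA-125, HE4, maximum SUV, peak SUV, two metabolic-volume thresholds and total lesion glycolysis gives seven terms. Fitted jointly, that is 25/7 = 3.6 events per term, or 25/8 = 3.1 with entry group. One marker plus entry group gives 25/2 = 12.5.

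**The case against.** The strongest case for the plan is that it answers the objectives as written. Objective 1.2.4 asks for a correlation and 1.2.6 asks whether parameters are predictive; an unadjusted odds ratio speaks to both. Value beyond histology is not a stated aim for these markers, and no decision in the plan depends on the odds ratios. This stands, and it is why the unadjusted estimate should be kept.

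A reader might infer that a marker which only separates high-grade from grade 1/2 tumours will appear to predict spread. The documents do not support that. Confounding needs spread to differ between the groups, and no group-specific rate is given. Patients in 3.1.2 enter because of deep invasion or cervical involvement, and section 2.0 counts depth as a risk factor too, so the difference could be nil or reversed. Even where it favours high grade, all four such intervals in the first table include 1.

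Section 2.0 also lists endometrial biopsy among pre-operative methods that predicted spread poorly, and its statement about nodal risk concerns final histology. Nor is the group read from the biopsy alone, since 3.1.2 also needs imaging or examination. These points may make entry group a weaker confounder. They do not remove the question, because the plan relies on the same pre-operative information for eligibility.

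Two limits of adjustment stand. A two-level term pools several histologies within 3.1.1, so some confounding may remain. And cervical involvement helps define 3.1.2 and may overlap with locoregional spread, so adjusting that model could remove real signal.

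**Conclusion.** The point holds as a conditional one. The planned models cannot separate a marker from entry group, although entry group is known before surgery and rests on factors that the protocol links to nodal risk. If spread differs between groups, in either direction, the unadjusted odds ratio may credit a marker that adds nothing or mask one that does. The illustrated distortion, from 0.73 through 1.0 to 1.92 for a two-level marker with no within-group effect, rests wholly on assumed group mix, spread rates and marker distributions. The chance of a spurious significant result is about 5% to 70% across the settings tried for a continuous marker with equal or higher spread in the high-grade group.

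This affects the interpretation of secondary objectives 1.2.4 and 1.2.6 and leaves the primary analysis untouched. It does not make the unadjusted odds ratio wrong for the question as worded. Nor does it give grounds for changing the scale on which markers enter or the type of correlation reported.

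**What to change.** In the Analysis part of 8.0, state that markers are fitted one at a time, and that for each the odds ratio with its 95% interval is reported twice: without and with a two-level term for entry group (3.1.1 versus 3.1.2). Keep the unadjusted value as the answer to the correlation asked for in 1.2.4. Use the adjusted value to judge whether a marker in 1.2.4 or 1.2.6 adds to pre-operative information. For locoregional spread, add a sentence that the adjusted result is read with caution because cervical involvement helps define 3.1.2.

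The cost is a few lines of wording. The data are already recorded at eligibility and no procedure changes. Statistically it takes one degree of freedom per model, with about 25 events by the node-positive proxy, and slightly wider intervals.
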